## **Amendments**

If the sponsor wishes to make a substantial amendment to the IRAS/HRA application or the supporting documents, the sponsor must submit a valid notice of amendment to the IRAS for consideration. The REC will provide a response regarding the amendment within 35 days of receipt of the notice. It is the sponsor's responsibility to decide whether an amendment is substantial or non-substantial for the purposes of the submission to the REC.

The amendment history will be tracked via version and date control of protocols, with changes to the protocol highlighted in Appendix 2.

## **9.3 Peer Review**

The funding for the study came from a competitive NIHR programme grant, which had a two-stage application process, and the scientific quality of the study was reviewed thoroughly by the funding panel as well as external scientific peer reviewers, who have provided comments and feedback which we have addressed.

Before submission, this protocol will be reviewed by the Chief Investigator ([name]) and the study sponsor (Noclor).

## **9.4 Patient and Public Involvement**

We will follow the NIHR guidelines on public involvement and maximising inclusion. We will establish a service user advisory group with five individuals with mild/ moderate ID from diverse backgrounds recruited using different strategies (e.g. existing links with ID services, charities, existing PPI groups, social groups, community day centres for ethnic minority groups) and we will assess whether we can use interpreters if needed. Our PPI lead will recruit service users to the advisory group and co-facilitate the groups with our PPIE co-applicant. As a speech and language therapist, our PPI lead has relevant skills in promoting inclusive communication with people with ID who may struggle to communicate verbally. Clinicians and carers will be involved in the co-production and adaptation groups in workstream 1. The groups will meet every three months (and more often during the initial stages).

Groups will run as hybrid meetings to enable accessibility for individuals less able to travel or living outside of London. Group members will be paid for their time, based on ELFT's reward and recognition policy, taking into consideration impact on benefits. Payment will cover preparation and attendance at meetings and transport costs. We will agree the terms of reference and responsibilities of the group. Carers will be paid for their time and travel expenses. We will follow guidelines on maximising PPI input and impact; We will record and measure PPI impact through feedback and interviews with advisory group members and the research team. The advisory group will:

- i. provide advice about study procedures (e.g. recruitment strategies)
- ii. be involved in the co-production group and adaptation group
- iii. co-produce information sheets, consent forms, recruitment posters and films; review topic guides
- iv. help train research assistants on interview techniques and obtaining consent
- v. review themes arising from qualitative data
- vi. support dissemination activities (producing accessible summaries of research, films, blogs, presenting at the dissemination seminar)
- vii. help produce training videos to train clinicians in using aDIALOG+ and attend training workshops

Our PPIE co-applicant will assist in undertaking qualitative interviews with participants with ID, and will receive supervision and training.

## **9.5 Protocol Compliance**

Protocol compliance will be ensured by the Chief Investigator. All cases of non-compliance or breach will be documented, with all major breaches reported to the Sponsor immediately.

## **9.6 Data Protection and Patient Confidentiality**

All investigators and study staff will comply with the requirements of the Data Protection Act 2018 and the General Data Protection Regulation (GDPR) with regards to the collection, storage, processing and disclosure of personal information and will uphold the Act's core principles throughout the study.

### *Personal Information*

Participants will be allocated a personal identification (ID) number and data will be pseudo-anonymised; all participant-related information will be stored separately from any identifiable study data. The research team will have access to personal data (e.g. names and contact details of participants) only if the participant has given permission for this information to be shared, and after the person has consented to take part in the study. We will only hold information that is necessary to enable us to contact the participant to arrange assessments, and some personal data will need to be collected as part of data collection (e.g. age, gender, ethnicity) but this will be pseudo-anonymised. The app supporting the aDIALOG+ intervention does not collect any identifiable information about the patients it is used with.

## *Pseudonymised Data*

Access to the electronic files and datasets for analysis will be restricted to the research team, and will be stored on password-protected databases / data safe havens. However, in the event of safety concerns, confidentiality will be broken and the relevant, services and/or authorities informed. For the qualitative component, audio-files will be transcribed by an approved transcription company, and stored in a data safe haven for analysis by the research team. The original files will be destroyed following transcription and completion of data analysis.

## **9.7 Indemnity**

The study will have indemnity through a standard NHS insurance scheme. The NHS indemnity scheme will cover the potential legal liability of the sponsor arising from the design, conduct and management of the study.

NHS indemnity does not offer no-fault compensation (i.e. for non-negligent harm), and NHS bodies are unable to agree in advance to pay compensation for non-negligent harm. They are permitted to consider an ex-gratia payment in the case of a claim.

Additionally, the feasibility study in care homes is covered by The Clinical Negligence Scheme for Trusts (CNST), which provides cover for NHS staff conducting research, whether that activity is taking place within NHS premises, patients' homes, care homes, hospices or other spaces in which NHS researchers undertake NHS research. ]

## **9.8 Access to the Final Study Dataset**

Only members of the research team will have access to the full dataset. Requests from external researchers to use the dataset for secondary analysis, may be made to the Chief Investigator.

## **10 DISSEMINATION POLICY**

### **10.1 Dissemination Policy**

East London NHS will own the data arising from this study.

The funders (NIHR) will be contacted at least 30 days prior to any publication arising from the project. Within publications, the funding body will be acknowledged using the standard text as set out within the research contract. A dissemination plan will be developed within the first 6 months of the study, with contributions from the sponsor and the PPI advisory group. The full study report will be produced when these grant-funded work packages are completed in November 2026.

We will work closely with our PPI advisory group to summarise the study findings into formats that are accessible for people with ID and their carers and will include co-produced newsletters, blogs, and film clips. A leaflet summarising the study findings will be made available to all the participating services and a copy will be sent to participants once the study results have been analysed and written up. We will also use social media such as X and Facebook to publicise the study findings.

### **10.2 Authorship Eligibility Guidelines and Any Intended Use of Professional Writers**

Authorship will be granted to co-applicants and researchers who worked on the project, dependent on their contributions.

## 12. APPENDICES

### 12.1 Appendix 1 – Required documentation

There will be an official invite to all sites which will contain the Local Document Pack, this will include all pertinent documents including the Organisation Information Document (OID), which will be completed collaboratively with the sites.

## 12.2 Appendix 2 – WP1a and b Schedule of Procedures

Procedures	1	2	3	4	5	6	7	8	9	10	11	12	13	14	15	16	17	18
	Jun 25	Jul 25	Aug 25	Sep 25	Oct 25	Nov 25	Dec 25	Jan 26	Feb 26	Mar 26	Apr 26	May 26	Jun 26	Jul 26	Aug 26	Sep 26	Oct 26	Nov 26
Recruitment of clinicians and care workers	x																	
Clinician and care worker training in aDIALOG+	x																	
Recruitment of service users		x																
Delivery of aDIALOG+ intervention		x																
Stakeholder focus groups/ interviews			x															
Data analysis and adaptations				x														
Recruitment of service users	x	x	x	x	x	x												
Baseline data collection	x	x	x	x	x	x												
Follow up	x	x	x	x	x	x												
Data analysis							x	x										

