For clinical services, eligible service users with ID will be identified from the case load of the participating clinician through the review of medical records. They will then be approached by the participating clinician or Clinical Studies Officer (CSO) to take part in the study and an information sheet will be provided. For care homes, eligible service users with ID will be identified from service records / clinical notes by care workers, and the research team will ask staff to approach eligible service users to take part in the study. If they are interested, their details will be passed to the research team, who will contact the potential participant, provide an information sheet, and assess their eligibility and capacity to consent. Service users will be eligible if they are aged 18 or over, have mild or moderate ID based on service records / clinical notes, have a current history of behaviour that challenges (at least one incident of self-injurious behaviour, physical aggression or damage to property in the last 3 months), are living in any setting including the family home and supported living/ residential home, and can provide informed verbal or written consent. We will ask clinicians and care workers to identify and approach all the service users on their caseload or within the care home, who are potentially eligible to take part, to take part in the study until they reach the recruitment target. This should reduce the likelihood of clinicians and care workers only approaching certain individuals to take part.

After 4-6 weeks we will invite the five clinicians, five care workers and at least ten service users to take part in separate stakeholder focus groups or interviews to obtain feedback on what aspects of the intervention (including the aDIALOG scale, app, training and manual) that worked well or did not work well and suggestions for improvement. Topic guides for the focus groups/interviews will be developed with input from the adaptation group (group of clinicians, carers and service users overseeing the work). We will also ask clinicians and care workers to complete the NoMAD questionnaire (39) for assessing implementation processes.

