## Data Collection

### 1. Work package 1a: Piloting adapted DIALOG+

After 4-6 weeks will invite the five clinicians, five care workers and at least ten service users to take part in separate stakeholder focus groups or interviews to obtain feedback on what aspects of the intervention (including the aDIALOG scale, app, training and manual) that worked well or did not work well and suggestions for improvement. The focus groups/interviews will be audio-recorded and transcribed. We will also ask clinicians and care workers to complete the NoMAD questionnaire (39) for assessing implementation processes from the perspective of professionals directly involved in the work of implementing complex interventions in healthcare.

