### 3. Work package 2: A feasibility study of delivering aDIALOG+ in clinical services

If service users are interested in taking part, the CSO or study research assistant will contact the person and their carer to discuss the study, will assess eligibility, obtain consent and conduct a baseline assessment, which will include completion of a socio-demographic and clinical data collection form (gender, age, ethnicity, severity of ID, neurodevelopmental conditions, day activities, living arrangements, co-morbid psychiatric and physical illnesses, prescribed medication (e.g. psychotropic medication), and psycho-social interventions that they have received or are receiving (e.g. positive behavioural support). Demographic information will also be collected from clinicians participating in the study (gender, age, ethnicity, profession, number of years in the service and years' experience working with people with ID) and participant carers (gender, age, ethnicity and education level). The aDIALOG+ app will capture data on the number of times aDIALOG+ was administered, changes in the aDIALOG scale scores over the duration of the intervention and goals set, but does not collect any identifiable information about the patients it is used with. Data on the number of sessions attended will be used to assess adherence to the intervention; we will analyse the mean changes in the scores for each domain on the aDIALOG scale.

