Statistical analysis (work package 1b): We will examine the distribution, variability and mean/median scores for each of the items. In order to assess concurrent and convergent validity, we will examine spearman's correlation between the items relating to subjective quality of life on the aDIALOG scale and the other measures. We will assess test re-test reliability by calculating the intra class correlation coefficient (ICC). Items that show poor distribution, variability and poor test re-test reliability may be removed from the scale. We will measure the internal consistency of the items relating to subjective quality of life and the treatment aspects separately using Cronbach's alpha.

Statistical analysis (WP 2 and WP 3): The feasibility outcomes will be the main focus of analysis and descriptive statistics, with associated measures of precision appropriately accounting for clustering, will be used to assess recruitment and retention, adherence, response rates in completing the outcome measures, demographic and clinical data, and cost data. We will explore changes in the scores of the outcome measures using paired t-tests or non-parametric tests where appropriate. The primary outcome measure of changes in behaviour will be measured using the Aberrant Behaviour Checklist (ABC)- irritability subscale (43). For secondary outcomes we will measure changes in behaviour (Behaviour Problems Inventory- short form) (53), quality of life (WHOQOL Disabilities module) (40), community participation (Guernsey Community Participation and Leisure Assessment – Revised) (44), psychological distress (Clinical Outcomes in Routine Evaluation, 14 item version) (42), psychiatric disorders (Moss Psychiatric Assessment Schedule - Check) (45), global improvement (Clinical Global Impression Scale) (46), health related quality of life (modified version of the EQ-5D-3L for people with ID) (48, 49) and service use (the Client Services Receipt Inventory) (51). The frequencies of adverse and serious adverse events will also be reported.

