In order to determine the minimal clinically important difference (MCID) for our primary outcome measure (ABC-I), we will compare changes in the ABC-I before and after aDIALOG+ and this will be linked to improvements in service users', care workers' or clinicians' ratings on the Clinical Global Impression Scale (global improvement measure). A change indicating that the patient is at least a "minimally improved" will be used as the cut-off score to indicate improvement. We will conduct sensitivity analyses to test different assumptions.

Qualitative data will be analysed using framework analysis to identify themes relating to the barriers and facilitators in implementing aDIALOG+ in clinical and care home settings and aspects of the intervention that need to be refined such as training, supervision and number and frequency of sessions. The focus groups/interviews will be audio-recorded and transcribed. We will use NVIVO to analyse the data using framework analysis to identify relevant themes relating to aspects of the intervention that did not work well and require further modifications, which will inform changes to the intervention. We will also ask clinicians and care workers to complete the NoMAD questionnaire (39) for assessing implementation processes from the perspective of professionals directly involved in the work of implementing complex interventions in healthcare.

Statistical analysis will be carried out on pseudo-anonymised data, and therefore personal identifiable data will not be published. For qualitative interviews, we will remove all

identifiable information from interview transcripts prior to analysis. Participants will be identified using a study ID in publications and we will take care not to present a combination of personal information together that could identify the person (e.g. age, gender, ethnicity).

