## 12.3 Appendix 2 – WP2 Schedule of Procedures

Procedures	1	2	3	4	5	6	7	8	9	10	11	12	13	14	15	16	17	18
	Jun 25	Jul 25	Aug 25	Sep 25	Oct 25	Nov 25	Dec 25	Jan 26	Feb 26	Mar 26	Apr 26	May 26	Jun 26	Jul 26	Aug 26	Sep 26	Oct 26	Nov 26
Recruitment of clinicians				X	X	X	X											
Clinician training in aDIALOG+				X	X	X	X											
Recruitment of service users					X	X	X	X	X									
Baseline data collection					X	X	X	X	X									
Delivery of aDIALOG+ intervention					X	X	X	X	X	X	X	X	X	X	X			
Follow up											X	X	X	X	X	X		
Stakeholder interviews											X	X	X	X	X	X		
Data analysis																	X	X

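### WP1b tests the aDIALOG scale in months 1-6, but the pilot that may revise the scale makes its adaptations only in month 4, and no version is fixed

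*Protocol*

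**What the plan says.** **Pilot (WP1a).** Section 5 of the protocol asks clinicians, care workers and service users for feedback on "aspects of the intervention (including the aDIALOG scale, app, training and manual) that worked well or did not work well and suggestions for improvement". The Data Storage and Analysis part of Section 5 says that the qualitative analysis will look for "aspects of the intervention that did not work well and require further modifications, which will inform changes to the intervention". The WP1a and b schedule (Appendix 2) puts the focus groups in month 3 (August 2025) and "Data analysis and adaptations" in month 4 (September 2025).

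**Psychometric testing (WP1b).** In the same schedule, recruitment, "Baseline data collection" and follow-up are all marked for months 1-6 (June to November 2025), with analysis in months 7-8. The statistical analysis text for WP1b adds: "Items that show poor distribution, variability and poor test re-test reliability may be removed from the scale".

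**Feasibility studies (WP2 and WP3).** Their schedules mark service user recruitment and baseline in months 5-9, "Delivery of aDIALOG+ intervention" in months 5-15, and analysis in months 17-18. For the aDIALOG scores, Section 5 states that "we will analyse the mean changes in the scores for each domain on the aDIALOG scale".

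**Before the study.** Section 5 describes five co-production workshops that produce a first adapted version, with possible changes to response format and wording. The readable text has no step that fixes the scale version before WP1b or before WP2 and WP3, and no rule for data collected on a superseded version.

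**The concern.** A validation study should be run on the instrument that will be used afterwards. Here the pilot and the validation run side by side, and the pilot is invited to criticise the scale that the validation is already measuring. If the pilot leads to a change in the scale, WP1b cannot deliver cleanly on objective 2 in Section 4.1, which is to establish whether aDIALOG is a useful quality of life measure in this population. Its reliability and validity estimates would describe either a mixture of two versions or a version that has been replaced.

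A similar overlap, with smaller consequences, exists downstream. The decision on which items to drop can come only after the WP1b analysis, by which time WP2 and WP3 have been collecting aDIALOG ratings for some months.

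**Working it through.** The plan states no figure on this point, so there is none to reproduce. The check compares the marked months and then counts participants by simple proportion. The protocol gives no monthly accrual, so even accrual over the marked recruitment months is an assumption.

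**Reading the schedule.** The rows of the WP1a and b table carry no work package label in the available text. The second block (recruitment, baseline, follow-up, analysis) must be WP1b, because WP1a has no baseline assessment and its own rows come first.

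| Activity | Months |
|---|---|
| WP1a focus groups and interviews | 3 |
| WP1a analysis and adaptations | 4 |
| WP1b recruitment, test and retest | 1-6 |
| WP1b analysis | 7-8 |
| WP2/WP3 service user recruitment and baseline | 5-9 |
| WP2/WP3 delivery | 5-15 |
| WP2/WP3 analysis | 17-18 |

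**WP1b participants tested before the pilot changes are complete** (120 planned, 6 months of accrual):
- before the adaptation month begins, months 1-3: 120 × 3/6 = 60;
- by the end of the adaptation month, months 1-4: 120 × 4/6 = 80;
- left for the version carried forward: 120 − 80 = 40 to 120 − 60 = 60.

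**What follows in each case.**
1. The pilot changes only the app, training or manual: WP1b is unaffected.
2. The scale changes and WP1b switches to the new version: 60 to 80 participants are on the old version and 40 to 60 on the new one. Item distributions, alphas and correlations pool the two. The retest is due within a week, so few test-retest pairs would straddle the change; the ICC suffers mainly from pooling pairs from different versions.
3. The scale changes but WP1b keeps the pre-pilot version: all 120 participants describe a version that is no longer in use.

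**WP2 and WP3 service users enrolled before item removal could be decided** (5 months of accrual):
- before the WP1b analysis begins, months 5-6: 30 × 2/5 = 12 in WP2 and 40 × 2/5 = 16 in WP3;
- by the end of that analysis, months 5-8: 30 × 4/5 = 24 in WP2 and 40 × 4/5 = 32 in WP3.

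Sessions are monthly for six months (at least monthly in WP3). With a first session in the month of enrolment, a person who starts in month 5 has sessions in months 5-10, and one who starts in month 8 has them in months 8-13. Both straddle the end of month 8. A domain withdrawn then would have a truncated series for these people.

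**The case against.** Several things can fairly be said for the plan.

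- *The harm is conditional.* A reader might infer that the WP1b data are bound to mix versions. The documents do not support that. The month 4 row does not name the scale, the feedback also covers app, training and manual, and item removal is worded as a possibility. This stands, and the point must be put conditionally. It does not remove the defect, because feedback on the scale is expressly sought and the plan cannot count on there being nothing to change.
- *The scale is not unadapted at month 1.* A reader might take month 4 to be the first adaptation. It is not; the workshops come earlier. This stands, and month 4 is a post-pilot refinement.
- *It may not be most of the sample.* Only months 1-3 lie wholly before the adaptation month, which gives exactly half. The range of 60 to 80 is the supportable statement.
- *The WP2/WP3 outcomes are separate instruments.* A reader might infer that outcome scores in general are contaminated. ABC-Irritability, WHOQOL-DIS and the other listed measures are not touched, and neither are recruitment and retention, the main purpose of WP2 and WP3. aDIALOG change is planned by domain, and in the parent DIALOG scale each domain is one rating. On that structure, dropping one domain shortens its own series and leaves the others comparable.
- *The flow charts are not available.* The absence of a version freeze can be asserted only for the readable text.
- *The study is exploratory.* WP1b is described as such, which lowers the stakes. It remains the only study here designed to validate the scale, and the Rationale (Section 2) leans on that validation.

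**Conclusion.** The sequencing problem holds in conditional form. If the post-pilot step changes the wording, response format or items of aDIALOG, about 60 to 80 of the 120 WP1b participants will have completed a superseded version, or all 120 if WP1b does not switch. Either way, objective 2 is not met for the version carried forward on the planned sample. The range rests on even accrual and on whether month 4 itself is counted.

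This is not a detail to leave to the statistical analysis plan. The order of data collection is set by the protocol, and no later analysis can recover answers to wording that was never administered. Splitting by version afterwards would leave about 40 to 60 people on the final version.

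The WP2/WP3 limb is minor: it is limited to any aDIALOG domain dropped during delivery, with about 24 of 30 and 32 of 40 service users enrolled by the time that decision could be made.

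**What to change.** 1. State in Section 5 that the aDIALOG wording, response format and item set are fixed at the end of the WP1a adaptation step (month 4).
2. Start WP1b testing on that version from month 5. Keeping the planned durations, testing would run in months 5-10 and analysis in months 11-12, still ahead of the WP2/WP3 analysis in months 17-18.
3. If WP1b must start earlier, or has already begun, record the version at each administration and report the psychometric results by version, with the version carried forward as the main result.
4. Keep the full fixed item set throughout WP2 and WP3, and apply any item removal arising from WP1b only in scoring at analysis. This rule is needed as well as the re-dating, because moving WP1b does not by itself settle what happens to items during delivery.

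**Cost.** WP1b would report about four months later (analysis moves from months 7-8 to months 11-12). Its 120 assessments and retests would overlap WP2/WP3 recruitment and baseline work in months 5-9, with research assistants needed for both. The protocol gives no staffing figures, so the team should check that this load is manageable; if it is not, option 3 is the fallback. The November 2026 end date need not change.
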